---

### Study Protocol

#### Purpose

1. Demonstrate the clinical effectiveness of transcranial direct current stimulation (tDCS) for patients with depression in real-world clinical settings.
2. Optimize home-based electroceutical technologies for patient-centered applications.
3. Generate real-world data (RWD) and evidence (RWE) to support the adoption of tDCS in clinical practice.

---

#### Design

##### 1. Overview:

- Randomized, double-blinded, multi-site clinical study.
- Participants: 198 adults aged 19–65 with mild to moderate major depressive disorder (MDD).
- Duration: 6 weeks of home-based self-applied tDCS.

##### 2. Device:

- MINDD STIM+ (YMS-201B+/201BS+), an FDA-approved tDCS device.

##### 3. Randomization:

- Group A: Active tDCS for 6 weeks.
- Group B: Active tDCS for 3 weeks followed by 3 weeks of sham stimulation.

##### 4. Primary Outcome Measures:

- Changes in BDI-II (Beck Depression Inventory-II) and MADRS (Montgomery-Åsberg Depression Rating Scale) scores from baseline (V1) to week 6 (V3).

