##### 5. Secondary Outcome Measures:

- HAM-A (Hamilton Anxiety Rating Scale) for anxiety.
- DSST (Digit Symbol Substitution Test) for cognitive function.
- CESD-R for daily depressive symptom assessment.
- qEEG (quantitative EEG) and HRV (heart rate variability).

---

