### Primary Statistical Methods

#### 1. Primary Analysis:

- **Dependent Variables:** Changes in BDI-II and MADRS scores from baseline to week 6.
- **Methodology:**
  - Independent t-tests to compare mean score changes between groups.
  - Mixed-effects models to adjust for repeated measures and site-level variation.

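### The primary comparison of V1-to-week-6 change carries patient-to-patient variation from three weeks of identical treatment; adjusting for V1 and a confirmed pre-switch score would narrow the A-B interval at little cost

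*Combined protocol and SAP*

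**What the plan says.** - **Arms** (Protocol, Design 3, Randomization): "Group A: Active tDCS for 6 weeks" and "Group B: Active tDCS for 3 weeks followed by 3 weeks of sham stimulation". The regimens are the same until the end of week 3. Design 1 (Overview) describes a "Randomized, double-blinded, multi-site clinical study".
- **Primary outcomes** (Protocol, Design 4): changes in BDI-II and MADRS "scores from baseline (V1) to week 6 (V3"). Only V1 and V3 are dated. The numbering implies a V2, but its timing and content are not given.
- **Primary analysis** (SAP, Primary Statistical Methods 1): "Independent t-tests to compare mean score changes between groups". Mixed-effects models for repeated measures and site are also listed, without visits, covariates or constraints.
- **Other measure before the switch** (Protocol, Design 5): "CESD-R for daily depressive symptom assessment". It is a secondary outcome and is given no role in the primary analysis.

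**The concern.** Weeks 1-3 work as a common active run-in. Any effect of allocation must arise in weeks 4-6, yet the compared quantity starts at V1. It therefore includes each patient's own course over three weeks of identical treatment: early response, natural course and regression to the mean. The average of that course cancels between arms, but its spread between patients does not. The spread stays in the standard error and widens the interval for the only contrast the design can inform.

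A score taken just before the switch would explain much of that spread. Under blinding and identical treatment, allocation cannot have affected it. V1 is three weeks too early to do the same job. What is at stake is precision and power, not validity.

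**Working it through.** **Inputs.** The total of 198 is from the Overview ("Participants: 198 adults aged"). It comes with no effect size, SD, alpha, power or dropout rate, so it cannot be reproduced and is used here only as the sample size. These are assumptions: 1:1 allocation (99 per arm), equal SDs at each visit, no dropout, two-sided 0.05, a measurement at week 3 (written as visit 2), and all correlations.

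**Formulas** (SD² units; r12, r13 and r23 are the correlations between V1, week 3 and week 6):

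- Change from V1: 2(1 − r13)
- Week 6 adjusted for V1: 1 − r13²
- Week 6 adjusted for V1 and week 3: 1 − R², with R² = (r13² + r23² − 2·r12·r13·r23) / (1 − r12²)
- 95% half-width for A-B: 1.96 × √(2 × variance / 99)

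**Base case** (r12 = 0.50, r13 = 0.40, r23 = 0.65):

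- Change: 2 × 0.60 = 1.20
- V1 only: 1 − 0.16 = 0.84
- V1 and week 3: R² = (0.16 + 0.4225 − 0.26) / 0.75 = 0.43, so 0.57

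| Analysis | Variance | Half-width (SD) |
|---|---|---|
| Change from V1 | 1.20 | 0.31 |
| Adjusted for V1 | 0.84 | 0.26 |
| Adjusted for V1 and week 3 | 0.57 | 0.21 |

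The total gain is 1.20 / 0.57 = 2.1. Of the reduction of 0.63, V1 adjustment alone supplies 0.36 (57%). The share due to the pre-switch score is 0.84 / 0.57 = 1.5.

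**Range.** Take r12 0.5-0.6, r13 0.3-0.5 and r23 0.5-0.8.

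- Most favourable corner (0.6, 0.3, 0.8): R² = (0.09 + 0.64 − 0.288) / 0.64 = 0.691. The variance is 0.309, which is 22% of the change-score variance (1.40) and 34% of the V1-adjusted variance (0.91).
- Least favourable corner (0.6, 0.5, 0.5): R² = (0.25 + 0.25 − 0.30) / 0.64 = 0.3125. The variance is 0.6875, which is 69% of 1.00 and 92% of 0.75.

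**CESD-R as the covariate** (correlation 0.4 with V1; r13 = 0.40):

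- Correlation 0.5 with week 6: R² = (0.16 + 0.25 − 0.16) / 0.84 = 0.298, variance 0.70
- Correlation 0.4 with week 6: R² = (0.16 + 0.16 − 0.128) / 0.84 = 0.229, variance 0.77

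Against 0.84 for V1 only, these are reductions of about 16% and 8%.

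**Power illustration** (assumed true difference 0.35 SD, r12 = r23):

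| r13, r23 | Change from V1 | V1-adjusted | V1 and week 3 |
|---|---|---|---|
| 0.3, 0.5 | 55% | 73% | 81% |
| 0.4, 0.6 | 61% | 77% | 87% |
| 0.4, 0.7 | 61% | 77% | 94% |
| 0.5, 0.7 | 69% | 81% | 93% |

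The pre-switch score adds about 8 to 17 points beyond V1 adjustment.

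**Bias check.** In 4,000 simulated trials (r12 = 0.7, r13 = 0.4, r23 = 0.7; true difference −0.35), the mean estimate was −0.346 for change from V1 and −0.350 for adjustment on both scores. The standard errors were 0.158 and 0.102. The target is the same and only the precision differs.

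**The case against.** Several stronger readings are tempting, and the documents do not support them.

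- **A week-3 BDI-II and MADRS exists and is ignored.** Nothing dates V2 or lists its assessments. The only documented measure likely to cover the days before the switch is the CESD-R, described as daily. It is a different scale, and its gain may be modest.
- **The mixed model ignores it.** Its terms are not given, so a model that uses week 3 would fit the wording. However, with complete data an unconstrained group-by-visit model reproduces the V1-to-V3 contrast and gains nothing from V2. The gain arises only if week 3 is a covariate or the arms are held equal through week 3, and that has to be written down.
- **Starting at V1 distorts the result.** It does not. Chance imbalance in early response is ordinary sampling error, already in the t-test's standard error, and type I error is not inflated.
- **The whole 2.1-fold gain belongs to this point.** More than half of the base-case variance reduction comes from V1 adjustment alone.
- **Measuring change from week 3 would be enough.** That gain is not assured. With SDs of 0.5, 1 and 1, r13 = 0.3 and r23 = 0.5, the variance goes from 0.95 to 1.00 (ratio 1.05). Covariate adjustment for week 3 in the same case gives 0.75 (ratio 0.79).
- **A post-randomisation covariate is always harmless here.** It is harmless only if taken before the switch. A score taken afterwards could absorb part of the effect.

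What stands of the case against is that the size is uncertain and the same-scale remedy depends on V2.

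**Conclusion.** The point holds as a matter of efficiency. The arms are identical for three of the six weeks, the listed t-test carries the variation of those weeks, and no pre-switch covariate is specified. The planned comparison is unbiased but less precise than it need be.

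With a same-scale week-3 score, the base case puts the value of that score at about 1.5 times the sample size beyond V1 adjustment. Across the range examined, it leaves 34-92% of the V1-adjusted variance, and the two adjustments together leave 22-69% of the change-score variance. With CESD-R instead, the variance is about 0.70-0.77 against 0.84. All of this rests on assumed correlations, equal SDs and 99 per arm. The direction is secure within those ranges, but the size is not. This is a worthwhile low-cost improvement, not a threat to validity.

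**What to change.** 1. State when V2 takes place relative to the switch and what is measured there, and confirm that CESD-R is completed daily.
2. Make the primary analysis the week-6 BDI-II and MADRS scores, each adjusted for the V1 score of the same scale and for the last pre-switch measurement. Use the V2 score of that scale if V2 collects it at or before the switch. Otherwise use mean CESD-R over the last week before the switch. A longitudinal model with the arms constrained equal through week 3 is an alternative.
3. Admit as covariates only scores dated before the patient's switch, or before the corresponding time point in Group A.
4. Impute missing covariate values, under the multiple imputation already planned, so that every ITT patient stays in.
5. Add one sentence explaining that the covariate is post-randomisation but precedes any difference in treatment.
6. Keep the unadjusted V1-to-V3 change as a supportive summary.

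**Cost:** SAP wording, some covariate imputation and a check of dates. No extra patients or visits are needed if existing V2 or CESD-R data are used.

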##### 5. Secondary Outcome Measures:

- HAM-A (Hamilton Anxiety Rating Scale) for anxiety.
- DSST (Digit Symbol Substitution Test) for cognitive function.
- CESD-R for daily depressive symptom assessment.
- qEEG (quantitative EEG) and HRV (heart rate variability).

---

#### Participant Criteria

- **Inclusion:**

- Age 19–65, mild to moderate MDD diagnosis.
- Informed consent capability.

- **Exclusion:**

- PTSD, psychotic MDD, severe suicidal risk, cranial implants, major cardiovascular or neurological issues.
- Prior tDCS use or participation in clinical trials within 30 days.

---

## Statistical Analysis Plan (SAP)

### General Overview

The statistical analysis will evaluate both primary and secondary outcomes based on intention-to-treat (ITT) and per-protocol (PP) populations.

---

### Primary Statistical Methods

#### 1. Primary Analysis:

- **Dependent Variables:** Changes in BDI-II and MADRS scores from baseline to week 6.
- **Methodology:**
  - Independent t-tests to compare mean score changes between groups.
  - Mixed-effects models to adjust for repeated measures and site-level variation.

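### Two primary methods are listed without choosing one, and the baseline score, already collected, is not named as a covariate; one designated baseline-adjusted model fixes both

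*Combined protocol and SAP*

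**What the plan says.** The SAP section Primary Analysis takes the change in BDI-II and in MADRS from baseline to week 6 as the dependent variables. It then lists two methods: "Independent t-tests to compare mean score changes between groups" and "Mixed-effects models to adjust for repeated measures and site-level variation". Neither is called the deciding analysis, and the fixed effects of the mixed model are not given.

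The SAP's General Overview says outcomes are evaluated "based on intention-to-treat (ITT) and per-protocol (PP) populations", again without ranking.

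The protocol section Primary Outcome Measures defines the endpoints as changes in "scores from baseline (V1) to week 6 (V3"), so a V1 score exists for everyone with a computable change. No section names that score as a covariate.

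The Randomization section gives Group A six weeks of active stimulation. For the comparator it says: "Group B: Active tDCS for 3 weeks followed by 3 weeks of sham stimulation".

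**The concern.** There are two linked gaps.

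**Designation.** Two methods and two populations give 2 × 2 = 4 candidate primary results for each scale. Where they differ, nothing in the SAP decides between them. A choice made after unblinding inflates type I error. The only multiplicity rule, Bonferroni, covers secondary outcomes.

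**Precision.** The change-score t-test is unbiased and keeps its type I error, but it fixes the coefficient of the V1 score at 1. A model that estimates the coefficient is generally more precise. This matters here because both arms receive the same active treatment for three weeks and differ only in weeks 4 to 6. The contrast is an increment on top of shared treatment and may be small.

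Whether the listed mixed model already recovers the lost precision depends on details the SAP does not give.

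**Working it through.** **Inputs from the documents.** 198 participants, two groups, endpoints at V1 and V3. The 198 cannot be reproduced, because no test level, power, effect, SD or dropout is stated.

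**Assumptions.** 1:1 allocation (99 per arm), two-sided 0.05, no dropout, correlation r between V1 and V3 of 0.3, 0.5 or 0.8, and SD ratio k = SD(V3)/SD(V1) of 1, 1.25 or 1.5. Ratios above 1 are included because entry is limited to mild to moderate depression, which may narrow the V1 SD.

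**Step 1: variance.** With SD(V1) = 1:
- change score: 1 + k² − 2rk
- baseline-adjusted: k²(1 − r²)
- share saved: (1 − rk)² / (1 + k² − 2rk)
- cost of estimating the slope: factor 1 + 1/(198 − 4) = 1.0052

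Example, k = 1 and r = 0.5: change 2 − 1 = 1.00; adjusted 0.75; ratio 0.75 × 1.0052 = 0.754.

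**Step 2: power.** 80% power for the t-test at 99 per arm needs a noncentrality of 2.815, which is a difference of 2.815 × √(2/99) = 0.400 SD of change. Dividing 2.815 by the square root of the variance ratio, with 195 degrees of freedom, gives the power of the adjusted model.

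**Step 3: disagreement.** The t-test and a baseline-adjusted model were simulated on the same data, 40,000 trials per setting.

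| k | r | Var. change | Var. adjusted | Ratio × 1.0052 | Power, adjusted | Methods disagree (effect present) | Either significant (no effect) |
|---|---|---|---|---|---|---|---|
| 1 | 0.3 | 1.400 | 0.910 | 0.653 | 0.934 | 14.9% | 7.6% |
| 1 | 0.5 | 1.000 | 0.750 | 0.754 | 0.897 | 12.5% | 7.5% |
| 1 | 0.8 | 0.400 | 0.360 | 0.905 | 0.838 | 7.4% | 6.5% |
| 1.25 | 0.3 | 1.813 | 1.422 | 0.789 | 0.884 | 11.3% | 7.0% |
| 1.25 | 0.5 | 1.313 | 1.172 | 0.897 | 0.841 | 7.5% | 6.5% |
| 1.25 | 0.8 | 0.563 | 0.563 | 1.005 | 0.798 | 1.2% | 5.4% |
| 1.5 | 0.3 | 2.350 | 2.048 | 0.876 | 0.849 | 8.8% | 6.6% |
| 1.5 | 0.5 | 1.750 | 1.688 | 0.969 | 0.812 | 4.3% | 5.9% |
| 1.5 | 0.8 | 0.850 | 0.810 | 0.958 | 0.817 | 4.9% | 6.0% |

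Each method alone had type I error of 4.8% to 5.3%. As a check on the last column, the two test statistics have large-sample correlation equal to the square root of the variance ratio before the 1.0052 factor. The bivariate normal distribution then gives 5.0% to 7.8% for either being significant, in line with the simulation.

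**Step 4: when adjustment loses.** It loses only if the share saved is below 1 − 1/1.0052, about 0.0051. Near rk = 1 this means |1 − rk| below about √(0.0051 × 0.5625) = 0.054 at k = 1.25, and √(0.0051 × 1.25) = 0.080 at k = 1.5.

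**Step 5: what the mixed model does.** In 2,000 simulated complete data sets (k = 1, r = 0.5), with arm means free at V1, the arm-by-visit contrast equalled the change-score difference (largest gap 2 × 10⁻¹⁶). With arm means constrained equal at V1, it equalled the baseline-adjusted estimate (largest gap 2 × 10⁻¹⁵), with a variance ratio of 0.74. The SAP does not say which form is meant.

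**The case against.** **The mixed model may already adjust for baseline.** It may, through a covariate or a common V1 mean. In that case adjustment adds nothing over that model. This stands, and it is why the gain against the mixed model is undetermined. It does not remove the need to say so in the SAP, because the listed t-test would then be the less precise of two undesignated methods.

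**The worst figures do not all apply together.** This is correct in part. If V1 means are free, neither listed method gains from baseline. With complete data and no site effect the two methods then coincide, so there is no disagreement and error stays near 5%. If the mixed model is adjusted, the disagreement figures apply and the loss of precision belongs to the t-test alone. On the free-means branch, site adjustment still separates the methods: a rough check assuming six sites and an intraclass correlation of 0 to 0.05 put either-significant error at about 5.5% to 6.1%.

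**The gain may be trivial.** Three of the six settings with an SD ratio above 1 save under 5%, and one of those three is slightly worse. The trade is still favourable: at most about 0.5% of variance lost, against up to 35% saved.

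**Two primary scales without an alpha rule are a larger leak.** If success on either scale were enough, two independent tests would give 1 − 0.95² = 9.75%. That is a separate gap. The error figures here are per scale, and this change does not close it.

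**Conclusion.** The point holds. It is certain from the text that no primary method or population is designated and that the V1 score is not named as a covariate. The t-test is not invalid; the issue is an open choice and precision probably given up.

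The size is uncertain. Against the t-test, under the stated assumptions, adjustment gives between 35% less and 0.5% more variance, and power between about 80% and 93% where the t-test has 80%. Against the mixed model the gain runs from none to the same amount, depending on its form. The cost of leaving the choice open, 1% to 15% disagreement and 5.4% to 7.6% type I error per scale, assumes that the second method is baseline-adjusted. Designation is worth making even if the precision gain is nil. The change should be made, but the trial does not fail without it.

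**What to change.** Before unblinding, amend the SAP section Primary Analysis to:

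- designate one primary model for each of BDI-II and MADRS;
- include a site effect and the V1 score of the same scale as a covariate, or constrain the arm means to be equal at V1;
- name the Group A minus Group B difference at week 6 (V3) as the primary estimate;
- state that ITT is the primary population, a choice the General Overview leaves open;
- keep the change-score t-test and the per-protocol analysis as supportive.

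The cost is SAP wording, a few lines of code and one degree of freedom, with no new data or participants. The documents do not give the trial's status, so it is an assumption that the change can still precede unblinding. An alpha rule across the two scales has to be settled separately.

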#### 2. Secondary Analysis:

- Evaluate changes in HAM-A, DSST, and CESD-R scores over time using regression analysis.

---

### Adjustments for Multiple Comparisons

To control for Type I error:

- Bonferroni correction for the analysis of multiple secondary outcomes.

---

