### Handling Missing Data

- Multiple imputation for missing data assuming data are missing at random (MAR).
- Sensitivity analysis to validate robustness.

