## Validation of Assumptions

1. **Normality:** Shapiro-Wilk test for residuals.
2. **Homogeneity of Variance:** Levene's test.
3. **Sphericity (if repeated measures):** Mauchly's test.

---

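### BDI-II and MADRS are both primary, but the plan gives no alpha, success rule or decisive analysis for them, so a split result can be called positive or negative.

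*Combined protocol and SAP*

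**What the plan says.** The protocol (Design, item 4, Primary Outcome Measures) lists "Changes in BDI-II (Beck Depression Inventory-II) and MADRS" scores as primary, measured from V1 to V3 at week 6. The SAP (Primary Statistical Methods, 1. Primary Analysis) repeats the pair as its dependent variables: "Changes in BDI-II and MADRS scores from baseline to week 6". Neither place orders the scales or says what result on the pair would count as success.

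Under the same SAP heading two methods stand side by side: "Independent t-tests to compare mean score changes between groups" and "Mixed-effects models to adjust for repeated measures and site-level variation". The General Overview adds two populations: "The statistical analysis will evaluate both primary and secondary outcomes based on intention-to-treat (ITT) and per-protocol (PP) populations". No method or population is given precedence.

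The section Adjustments for Multiple Comparisons has one item: "Bonferroni correction for the analysis of multiple secondary outcomes". No significance level or sidedness appears in the available text. Handling Missing Data provides for multiple imputation without saying which of the listed analyses uses the imputed data.

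**The concern.** The plan recognises multiplicity and deals with it for the secondary outcomes, but not for the two outcomes that carry the conclusion. Suppose one scale reaches significance and the other does not. If a win on either scale is enough, the trial is positive; if both are needed, it is negative. Nothing in the plan settles which, so the choice can be made with the results in view.

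The method and the population are open too. Two scales × two methods × two populations give up to 2 × 2 × 2 = 8 primary p-values, with no rule for which of them count. The protocol's first stated purpose is to demonstrate effectiveness in a randomised, double-blinded study, and a claim of that kind needs a success criterion fixed in advance.

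**Working it through.** **Inputs.** From the documents: two primary scales, two arms and 198 participants (protocol, Design). Assumed, because the documents do not give them: two-sided 0.05 per scale, 99 per arm, no dropout, the same standardised effect d on both scales, and a range of between-scale correlations ρ.

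**The plan's own figure.** The 198 cannot be reproduced, because no effect size, SD, alpha or power accompanies it. For one test at two-sided 0.05 with 80% power and d = 0.40, n per arm = 2(1.960 + 0.842)²/0.40² ≈ 98.1, rounded up to 99, or 198 in total. That matches assumed inputs only; it does not show what the authors intended.

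**Error with no true effect.** With independent scales, P(at least one significant) = 1 − 0.95² = 0.0975. With correlation, P(at least one) = 2 × 0.05 − P(both), and P(exactly one) = 2 × 0.05 − 2 × P(both), with P(both) from the bivariate normal.

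| ρ | P(both) | At least one at 0.05 | Exactly one |
|---|---|---|---|
| 0 | 0.0025 | 0.0975 | 0.0950 |
| 0.5 | 0.0093 | 0.0907 | 0.0815 |
| 0.9 | 0.0296 | 0.0704 | 0.0407 |
| 0.95 | 0.0354 | 0.0646 | 0.0291 |

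(The last column was computed before rounding, so it can differ by 0.0001 from the rounded inputs.)

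At 0.025 per scale, which is Holm's first step, P(at least one) is 0.0494 at ρ = 0 and 0.0330 at ρ = 0.95, so Holm holds 0.05. If both scales must be significant at 0.05, the error is at most 0.05. It approaches that limit when one scale has a large effect and the other none.

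**Power and split results.** Bivariate t simulation, 1,000,000 replicates, 99 per arm, 196 degrees of freedom. Split means exactly one scale significant at 0.05, that is, either minus both.

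| d | ρ | One scale | Either | Both | Split | Holm, at least one | Holm, a given scale |
|---|---|---|---|---|---|---|---|
| 0.30 | 0.5 | 0.556 | 0.721 | 0.390 | 0.331 | 0.607 | 0.491 |
| 0.30 | 0.9 | 0.556 | 0.628 | 0.485 | 0.143 | 0.514 | 0.485 |
| 0.40 | 0.5 | 0.800 | 0.913 | 0.686 | 0.227 | 0.851 | 0.763 |
| 0.40 | 0.9 | 0.800 | 0.850 | 0.750 | 0.100 | 0.773 | 0.750 |
| 0.50 | 0.5 | 0.938 | 0.984 | 0.892 | 0.091 | 0.966 | 0.927 |
| 0.50 | 0.9 | 0.938 | 0.960 | 0.917 | 0.043 | 0.927 | 0.917 |

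A separate normal-approximation calculation gives split probabilities of 0.223 and 0.099 at d = 0.40, in line with the simulation.

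**Methods and populations.** The plan says too little about the mixed model and the PP set to size the effect of choosing among them. The eight p-values would be strongly correlated, so no family-wise figure is claimed for them.

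**The case against.** The strongest reply is that the scales are joined by a plain conjunction, which may mean that both must succeed. On that reading the error is at most 5% and no primary adjustment is needed. This stands as far as it goes: inflation is not proven. But the plan does not say so, and that reading still leaves alpha, method and population unstated.

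A second reply is that both scales measure depression in the same patients at the same visit, so 9.75% is an upper bound. The 33% split chance also needs d = 0.30 and ρ = 0.5, where single-scale power is only 56%. Both points are fair. Even at ρ = 0.9, however, the either-scale error is 7.0%, and split results run from 4% to 14% across d = 0.50 to 0.30.

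Third, ITT and PP may be listed together simply so that both are reported, and unrestricted imputation wording may be meant to cover every analysis. That is possible. The imputation remark is a clarification only, and the finding does not rest on it.

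Fourth, a baseline covariate is not needed for error control. That is correct; it is proposed for precision. The SAP's dependent variable is change from baseline, so baseline would not enter twice as a response.

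**Conclusion.** The concern holds. The defect is the missing rule, which follows from the text and depends on no assumed figure. Under the stated assumptions, counting a win on either scale without adjustment gives 9.75% to 6.5% family-wise error (ρ from 0 to 0.95), against at most 5% if both are required. The outcome on which the two readings disagree has an 8% to 4% chance with no effect, 33% to 14% at d = 0.30, 23% to 10% at d = 0.40 and 9% to 4% at d = 0.50 (ρ = 0.5 to 0.9). The open choice of method and population adds to this by an amount that cannot be sized. The gap can change the headline conclusion and cannot be credibly closed after unblinding, so it must be fixed before then.

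**What to change.** Before unblinding, amend the SAP as follows.

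- **Adjustments for Multiple Comparisons:** state an overall two-sided alpha of 0.05 for the primary family and one rule. Use Holm across BDI-II and MADRS if either scale can establish success; otherwise require both scales to be significant at 0.05.
- **General Overview and Primary Analysis:** name as decisive, for each scale, the week-6 group contrast from the mixed-effects model already listed, with the baseline score as a covariate, in the ITT population. State that the t-test and PP results are supportive. Naming the t-test as decisive would close the error-control gap equally well; the mixed model is suggested because the SAP already relies on it for site variation.
- **Handling Missing Data:** state whether the decisive model uses the imputed data.

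The cost is wording and some power. At d = 0.40 and ρ = 0.5 to 0.9, Holm takes power on a given scale from 80% to 76–75%, and the chance of at least one win from 91–85% to 85–77%. Requiring both scales gives 69–75%. At d = 0.30 the corresponding figures are 56% to 49%, 72–63% to 61–51%, and 39–48%. At d = 0.50 they are 94% to 93–92%, 98–96% to 97–93%, and 89–92%.

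Baseline adjustment may recover some of this. Relative to unadjusted change, the variance gain is (1 + k² − 2rk)/(1 − r²), where r is the baseline to week-6 correlation and k the ratio of baseline SD to week-6 SD. Neither is in the documents. Illustrations:

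- r = k = 0.7: 0.51/0.51 = 1.00
- r = 0.5, k = 0.8: 0.84/0.75 = 1.12
- r = 0.3, k = 1: 1.40/0.91 = 1.54

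Single-scale power at d = 0.40 is then 80%, 84% and 93.5% respectively.

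### Holm's step-down procedure could replace Bonferroni for the secondary outcomes: same familywise error, never fewer rejections, and a gain that depends on how many outcomes respond

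*Combined protocol and SAP*

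**What the plan says.** The SAP section Adjustments for Multiple Comparisons gives its aim as "To control for Type I error" and then one rule: "Bonferroni correction for the analysis of multiple secondary outcomes". It states no alpha, number of tests, list of outcomes or stepwise element. The ordinary reading is that each secondary outcome is tested at alpha divided by the number of outcomes, m.

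The value of m depends on the section consulted. The SAP's Secondary Analysis names three scores: "Evaluate changes in HAM-A, DSST, and CESD-R scores over time using regression analysis". The protocol's Secondary Outcome Measures lists those three plus qEEG and HRV, so at least five. No power target or success criterion is attached to any secondary outcome, and no simultaneous confidence intervals are planned.

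**The concern.** Single-step Bonferroni holds every outcome to the strictest threshold, alpha/m, even after other outcomes have been rejected. Holm relaxes the threshold after each rejection without raising the familywise error. If several secondary outcomes truly respond, the plan as written can leave some of them short of significance when an equally rigorous procedure would have declared them.

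What is at stake is the secondary evidence on anxiety, cognition and daily depressive symptoms, and possibly on qEEG and HRV. The primary analysis of BDI-II and MADRS is not affected.

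**Working it through.** **Inputs from the documents.** Total sample 198 (protocol, Overview); two arms (Randomization); m = 3 (SAP, Secondary Analysis) or m = 5 (protocol, Secondary Outcome Measures, counting qEEG and HRV once each).

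**Assumptions, because the documents are silent.** 1:1 allocation, so 198/2 = 99 per arm; two-sided familywise alpha 0.05; no dropout; standardised between-group difference d = 0.4 on each responding outcome, with 0.2 to 0.5 as the range; equal correlation between outcomes, 0 to 0.8. Each test is treated as a two-sample comparison with standard error √(2/99). The SAP says only regression over time, so this is an approximation. The plan has no figure of its own to reproduce.

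**Thresholds.** Bonferroni compares every p-value with 0.05/m. Holm orders the p-values and compares the i-th smallest with 0.05/(m − i + 1), stopping at the first failure.
- m = 3: Bonferroni 0.0167 throughout; Holm 0.0167, 0.025, 0.05.
- m = 5: Bonferroni 0.01 throughout; Holm 0.01, 0.0125, 0.0167, 0.025, 0.05.

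No Holm threshold is below the Bonferroni one, so Holm keeps every Bonferroni rejection. For error control, suppose m0 null hypotheses are true. When Holm first rejects a true null, at most m − m0 hypotheses have already been rejected, so the threshold is at most 0.05/m0. By the union bound the familywise error is at most m0 × 0.05/m0 = 0.05, whatever the correlation.

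**Power per outcome under Bonferroni.** Power = Φ(d/√(2/99) − z), where z is the two-sided critical value at 0.05/m. With d = 0.4, d/√(2/99) = 2.814.
- m = 3: z = 2.394, so Φ(0.420) = 0.663.
- m = 5: z = 2.576, so Φ(0.238) = 0.594.

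**Bonferroni against Holm by simulation** (400,000 replicates for most rows, at least 200,000 for all; d = 0.4; average power per responding outcome):

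| Outcomes responding | Correlation | Bonferroni | Holm | Gain (points) |
|---|---|---|---|---|
| 1 of 3 | 0 | 66.3% | 66.5% | 0.2 |
| 1 of 5 | 0 | 59.5% | 59.7% | 0.2 |
| 2 of 3 | 0.5 | 66.3% | 69.5% | 3.2 |
| 2 of 5 | 0.5 | 59.5% | 61.2% | 1.7 |
| 3 of 5 | 0.3 | 59.4% | 63.3% | 3.9 |
| 3 of 3 | 0.5 | 66.3% | 73.9% | 7.6 |
| 5 of 5 | 0.5 | 59.5% | 69.2% | 9.7 |

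The one-responder gain falls to about 0.1 point or less as correlation rises. Two of three at correlation 0 gives 3.8 points.

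**Showing every outcome.** With correlation 0.5, the chance of rejecting all three goes from 42% to 60%, and all five from 25% to 49%.

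**At least one rejection.** This is identical under both methods (88% for three of three, 90% for five of five, correlation 0.5), because the smallest p-value meets the same 0.05/m threshold.

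**Role of correlation.** With all three affected and d = 0.4, the average gain is 9.2, 8.2, 7.6 and 6.5 points at correlations 0, 0.3, 0.5 and 0.8. It falls as correlation rises.

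**Role of effect size.** With all three affected, the gain is 1.5 to 3.4 points at d = 0.2 (correlation 0 to 0.8). At correlations 0 and 0.5 it is about 6 points at d = 0.3 and 5 to 6 at d = 0.5.

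**Error check.** Holm's simulated familywise error stayed below 0.05 in every scenario with at least one true null.

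**The case against.** The strongest reply is that this is a preference. Bonferroni is valid: it causes no bias and no type I inflation, and no stated goal is missed because the secondary outcomes carry no power target. That stands, and it fixes the level of the point. It does not remove the gain, because the direction of the comparison needs no assumption.

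A reader might infer that power is being given away for nothing. That goes too far. Single-step Bonferroni gives simultaneous intervals that agree with its tests, and Holm does not readily do so. An outcome rejected only by Holm could have a Bonferroni-level interval that includes zero. The cost is real but small here, since the plan announces no simultaneous intervals.

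A reader might also infer that the gain is substantial as soon as more than one outcome responds, or largest where outcomes move together, as anxiety and daily symptoms may. Neither is supported. Two responding outcomes give about 2 to 4 points, and at d = 0.4 the gain shrinks as correlation grows. Only at small effects such as d = 0.2 does it rise with correlation, and there it stays below 4 points.

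The larger figures need every outcome, including cognition and the physiological measures, to respond at d = 0.4. Under the protocol's Randomization section the comparator is "Group B: Active tDCS for 3 weeks followed by 3 weeks of sham stimulation", so both arms are active for the first three weeks and the planned contrast arises in weeks 4 to 6. A uniform 0.4 may be optimistic.

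Finally, the undefined family, the unstated alpha and the lack of a rule for the two primary outcomes are arguably weightier gaps. They are separate points, but one bears directly on the fix: Holm's thresholds depend on m just as Bonferroni's do, so the family must be named.

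**Conclusion.** The point holds as an optional improvement. Bonferroni as planned is valid; Holm controls the same familywise error under any dependence and never rejects less. That comparison is exact. Its size is not derivable from the documents and rests on the assumptions listed (99 per arm, two-sided 0.05, d = 0.4, no dropout, two-sample tests).

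On those assumptions the gain runs from a negligible 0.1 to 0.2 points with one responding outcome to about 10 points with all five at correlation 0.5. With all three it is roughly 7 to 9 points over the correlations examined. The main driver is the number of outcomes that respond. Nothing here shows an error in the plan or a threat to the primary result.

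**What to change.** Replace the Bonferroni sentence with:

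> The secondary outcomes HAM-A, DSST and CESD-R (and qEEG and HRV parameters, if they are to be tested confirmatorily) will be tested with the Holm step-down procedure at two-sided familywise alpha 0.05; Holm-adjusted p-values will be reported.

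If qEEG and HRV are included, list each parameter so that m is fixed. Make the change before unblinding.

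For intervals, either report unadjusted 95% confidence intervals labelled as such, or report Bonferroni-level intervals with a note that they may include zero for an outcome rejected only by Holm.

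The cost is one SAP sentence and one software option, plus the less direct link between tests and simultaneous intervals. No data collection or sample size changes.
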